2.4 Rationale

The central thesis of this protocol is that an inhibitor of IDO1 may decrease melanoma-associated immune suppression and immune cell-associated immune suppression and increase the immune response at sites of tumor, specifically increasing both the total number of T cells and the number of melanoma antigen-specific T cells infiltrating the tumor. IDO expression and function arises from 2 potential sources: (1) tumors can overexpress IDO and (2) inflammatory cells can upregulate IDO in response to the IFN-gamma secreted by activated T lymphocytes. Overexpressed and upregulated IDO subsequently depletes tryptophan and increases tryptophan catabolites, including kynurenine, that cause antigen-presenting cells (APCs) and cytotoxic T cells to be ineffective against established tumors. Data from animal experiments [[Munn 2012](#)] demonstrate that IDO induction after vaccination serves as a negative feedback loop that dampens the immune response to dendritic cell-based cancer vaccines. An effective IDO inhibitor may reverse this particular form of tumor-associated immune suppression and increase the response to tumor vaccines by augmenting T-cell responses to cancer antigens.

A relatively nontoxic regimen of INC024360 as monotherapy has been shown to normalize serum Kyn/Trp ratios in patients with cancer. That same regimen is hypothesized to inhibit the effect of IDO expression at sites of tumor deposition and thereby unleash the nascent or vaccine-induced antitumor immune response either at sites of tumor deposition or in the tumor-draining lymph nodes. In addition, the same regimen is hypothesized to increase the systemic immune response to cancer vaccines and/or allow vaccine-induced T cells to replicate and to function better at sites of tumor deposition. Because the melanoma multiple peptide vaccine, MELITAC 12.1, stimulates immune responses, has an excellent safety profile, and is presumed efficacious in the adjuvant setting, treating patients with INC024360 *before* vaccination with MELITAC 12.1 might increase the immune response to antigens expressed by melanoma cells and allow for an increased antitumor immune response.

2.4.1 IDO Inhibition in Melanoma and T-cell Infiltration into Tumor

IDO is strongly associated with poor prognosis [[Gajewski 2005](#); [Brody 2009](#)], and dendritic cells in lymph nodes draining melanomas express IDO [[Lee 2003](#)]. High expression of IDO in the sentinel nodes of patients with melanoma is strongly associated

with increased tumor burden and shorter survival [[Lee 2011](#); [Speeckaert 2012](#)]. On the other hand, a recent biomarker study found that high IDO expression in tumors before treatment was associated with improved outcome after therapy with ipilimumab, and that increases in T-cell infiltration during treatment were also associated with improved clinical outcome [[Hamid 2011](#)].

IDO is induced by IFN-gamma produced by T cells, and thus represents a potent immune regulatory pathway induced when activated T cells infiltrate tumors [[Mackler 2003](#); [Zhang 2011](#); [Zhao 2012](#)]. The findings from this recent study emphasize the highly complex interplay of immune activation and suppression in the melanoma microenvironment and its association with T-cell infiltration. They suggest that patients whose tumors express high levels of IDO are those with immune signatures for whom an immune therapy may have a higher chance of success, and that clinical benefit is associated with an increase in T-cell infiltration of melanoma metastases.

2.4.2 Lymphocyte Infiltrates

Patients with brisk lymphocytic infiltrates in primary melanomas have lower risk of metastasis and death than patients with sparse or absent infiltrate [[Erdag 2012](#)]. In addition, [name] has established that lymphocytic infiltrate in metastatic melanomas correlates with increased survival. [name] evaluated the composition and organization of immune cells that infiltrated 183 melanoma metastases in humans. CD45+ cell counts ranged from 0 to 2,142 per mm² (Table 2.4.2). The most prevalent immune cells in the first metastases were T cells (53%), of which CD8+ T cells predominated (35%) and CD4+ T cells were less common (19%). B cells (CD20) and plasma cells (CD138) were present at high numbers (25% and 8%, respectively). Macrophage lineage cells (CD163) accounted for 13% of the infiltrates. NK cells (CD56) and mature dendritic cells (DC-LAMP) were rare across all samples, with mean proportions of less than 1% each.

Table 2.4.2. Distribution of Immune Cell Subsets Among 183 Metastases Studied [[Erdag 2012](#)]

Subset	N	Mean	Min	25%	Median	75%	Max
CD45	183	246	0	31	117	343	2142
CD138	183	26	0	0	2	23	488
CD20	182	65	0	0	5	47	1796
CD3	183	153	0	20	83	226	1049
CD4	183	52	0	3	16	60	602
CD8	182	103	0	15	71	153	462
CD56	183	3	0	0	0	2	85
PD1	183	18	0	0	2	20	262
Foxp3	182	19	0	0	8	23	175
CD163	182	39	0	2	18	53	360
DC-LAMP	1	0	0	0	0	1	19

Three histologic patterns of immune cell infiltration were identified. Immunotype A was characterized by no immune cell infiltrate. Immunotype B was characterized by infiltration of immune cells limited only to regions proximal to intratumoral blood vessels. Immunotype C was characterized by a diffuse immune cell infiltrate throughout a metastatic tumor. These

immunotypes represented 29%, 63%, and 8% of metastases with estimated median survival periods of 15, 23, and 130 months, respectively. The best correlates with survival were with CD8+ T cells. Whereas higher densities of CD8+ T cells correlated best with survival, a higher density of CD45+ leukocytes, T cells, and B cells also correlated with increased survival. These reveal how the immune microenvironment can affect outcomes and also provide a method to quantify the effect of the IDO1 inhibitor on immune cell infiltration.

2.4.3 **Data on combination effects of checkpoint blockade antibodies and IDO inhibition.**

The success of checkpoint blockade therapy for melanoma has transformed the management of patients with advanced melanoma, but most patients treated with antibodies to CTLA4 or PD-1 will progress despite those therapies. Combined therapy with antibodies to CTLA4 and PD-1 have induced higher response rates, and durable clinical benefit, but at the price of increased toxicity. There is a need for additional combination therapies that may enhance clinical benefit, ideally at lower toxicity than combination of CTLA4 and PD-1 antibodies. IDO and PD-1 can mediate immune escape of melanoma. As effector T cells infiltrate melanoma metastases, they produce interferon-gamma, which in turn can induce both PD-L1 and IDO. Blockade of PD-1/PD-L1 can further increase T cell infiltration; so there is rationale to expect that IDO may mediate progression of cancer on PD-1 antibody therapy. [[Spranger 2015](#)], [[Gajewski 2015 patent](#)]

Combination of ipilimumab and the IDO inhibitor INCB024360 has induced significant transaminase elevations in 5 of 7 patients, when INCB024360 was administered at 300 mg bid; the study was continued in 8 patients at a much lower dose of INCB024360 (25 mg bid), with disease control observed in 6 of those 8 patients and irPR in 3 (38%). Thus, this small series suggests encouraging clinical outcomes with that combination, but there was unacceptable toxicity with a higher dose of INCB024360. Treatment of patients with another IDO inhibitor (D-1MT) after prior ipilimumab also was associated with dramatic toxicities, including hypophysitis, also raising questions about the toxicity of CTLA-4 blockade plus IDO inhibition.

PD-1 blockade with pembrolizumab or nivolumab has become standard first-line therapy for advanced melanoma (based on data reported in 2015); yet most patients treated with these agents will progress on therapy. Addition of IDO inhibition to these patients offers promise for improving clinical response rates, thus, a cohort has been added to allow addition of INCB024360 early after the last dose of PD-1 antibody (or PD-L1 antibody). If data from this cohort support safety and clinical activity of INCB024360 when added to patients progressing on PD-1 antibody, these data will support future study of adding INCB024360 while continuing PD-1 antibody after failure to respond. Also, biopsies obtained after progression on PD-1 antibody and after adding INCB024360 will provide insight into the role of IDO in mediating failure of PD-1 inhibition and the changes in the tumor microenvironment of adding IDO blockade while PD-1 blockade remains active.

2.4.4 Correlative Studies

To meet the primary objectives, tumors will be biopsied before therapy, after 3 weeks of INC024360 treatment, and 1 week after the third vaccine plus INC024360. Because immunotype and immunohistologic characteristics of tumor-infiltrating immune cells are associated with clinical outcome in metastatic melanoma [[Erdag 2012](#)], tumors will be assessed by IHC for T-cell infiltration patterns and infiltration with cells expressing CD8. CD8+ T cell infiltration will be reported as cells per mm² of cross-sectional tumor area.

Note: Optimally, patients will have tumor approachable for three serial biopsies during the trial. For patients with only one or two tumors approachable for biopsy, available tumor blocks from prior biopsies (without intervening systemic treatment) can serve as the pretreatment sample. The biopsy after 3 weeks of INC024360 will be considered essential. Biopsy 1 week after the third vaccine plus INC024360 will be considered optional.

To characterize the immune cell infiltrate further, the tumors will also be assayed for a variety of antigens including CD4, CD8, CD56, CD34, CD45, CD20, CD3, CD8, CD138, CD163, DC-LAMP, FoxP3, and PD-1. IHC staining of tumor biopsies will also be performed to detect IDO1 expression, and the presence and patterns of CD8+ and CD4+ T cell infiltration, Foxp3 protein, and FoxP3 Treg infiltration. Gene signature will be assessed using an Affymetrix chip with focus on IFN signaling, IDO expression, and tumor rejection [[Weiss 2011](#)] with each patient serving as their own control. Gene signatures on the tumor will be determined by [name], and [name], Chief, Infectious Disease and Immunogenetics Section in the Department of Transfusion Medicine, Clinical Center of the National Institutes of Health.

A number of other (secondary) correlative studies will be conducted to evaluate whether a regimen of INC024360 that normalizes serum Kyn/Trp ratios plus MELITAC 12.1 vaccine changes the level or character of the vaccine-induced CD8+ and CD4+ T-cell immune responses as measured in peripheral blood, compared to each patient's baseline. Evaluations will occur at baseline (week 0), again at week 3, week 6, some are done at week 14 and they are repeated optionally at week 16 only if the optional biopsy is done at week 16. Effector 8+ T-cell responses to MELITAC 12.1 will be measured by IFN-gamma enzyme-linked immunosorbent spot assay (ELISpot) and with tetramers/multimers to 8 of the peptides in the vaccine. Effector CD4+ T-cell responses to MELITAC 12.1 will also be tested. Assays will be performed in the CITN Central Laboratory of the Tumor Vaccine Group led by [name], in collaboration with the immune monitoring laboratory of [name].

The extent to which INC024360 plus MELITAC 12.1 vaccine alters the number and character of PBMC (including T and NK cells as evaluated by multiparameter flow cytometry) will be calculated by assessing the effect on T lymphocyte number and phenotype (i.e., CD8+, effector memory CD8+, central memory CD8+, CD4+, CD4+ Treg, naïve subsets). The frequency and percentage of PBMC subsets will be determined using multiparameter flow cytometric analysis on whole blood. The markers include

CD3, CD8, CD4, CD56, Foxp3, CD127, CD45RA, CD45RO, CCR7, CD28, CD27, CD25, CD122, CD86, CD14, CD16, CD19, CD123, and CD11c. Changes in myeloid-derived suppressor cell populations will also be assessed by flow cytometry. Assays will be performed in the CITN Central Laboratory of the Tumor Vaccine Group led by [name], in collaboration with the immune monitoring laboratory of [name].

3. PATIENT SELECTION

3.1 Eligibility Criteria

- 3.1.1 Patients must have malignant melanoma validated by histology or cytology. Patients may have had primary cutaneous, mucosal, or ocular melanoma or metastasis from an unknown primary site.

NOTE: Patients must have measurable disease, defined as at least 1 lesion that can be accurately measured in at least 1 dimension (longest diameter to be recorded for non-nodal lesions and short axis for nodal lesions) as ≥ 20 mm with conventional chest x-ray or as ≥ 10 mm with spiral computed tomography (CT) scan, magnetic resonance imaging (MRI), or calipers by clinical exam. See [Section 11](#) for the evaluation of measurable disease.

- 3.1.2 Unresectable stage III or IV melanoma validated by clinical criteria (including recurrent melanoma), or patients with multiple skin/soft tissue metastases of melanoma that may be resectable but are judged to have a future recurrence risk exceeding 70% (e.g., large adenopathy, distant skin metastases or multiple in-transit melanoma metastases). Tumor deemed amenable to biopsy (excisional, incisional, or core, with at least 100 mm³ tumor volume per biopsy date) and fine-needle aspiration (FNA) biopsy.

Note: Optimally, patients will have tumor approachable for three serial biopsies during the trial. For patients with only one or two tumors approachable for biopsy, available tumor blocks from prior biopsies can serve as the pretreatment sample, but only if formalin-fixed tumor tissue is available and adequate to provide at least 20 unstained slides with sufficient tumor for analysis.

NOTE: Patients with unresectable advanced stage III or IV melanoma (including recurrent melanoma) are only eligible if they have failed at least one other first-line systemic therapy (other than adjuvant therapy). Exceptions to this requirement are those patients who have refused and/or are ineligible for other systemic therapies.

NOTE: BRAFi should be considered for all ‘unresectable’ or metastatic melanoma with BRAFV600E mutation; for low burden in-transit disease patients may enter trial without prior systemic therapy.

- 3.1.2.1 Stage IV no evidence of disease (NED) is excluded by this criterion

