3.1.3 Prior and concurrent therapy

- 3.1.3.1 Patients may have had prior systemic therapy without constraint on the number of prior treatment regimens except:
- a) Patients may not have had $>450 \text{ mg/m}^2$ doxorubicin
 - b) Patients may not have had $>3000 \text{ cGy}$ to fields encompassing the entire pelvis
- 3.1.3.2 Patients must not be on any other systemic therapy within the following intervals before study enrollment:
- a) 1 week after stereotactic radiosurgery of the brain or comparable technology
 - b) 4 weeks after cytotoxic chemotherapy or external beam radiation therapy
 - c) 6 weeks after chemotherapy regimens including BCNU (carmustine) or mitomycin C
 - d) patients who experience melanoma progression (by RECIST 1.1 criteria) while on or after treatment with PD-1 or PDL-1 antibody may enroll on this study.

NOTE: Patients must be off PD-1/PDL-1 antibody for at least 2 weeks to assess for delayed toxicity before being enrolled and receiving INCB024360. Patients who are enrolled 2 weeks and up to 6 weeks after the last dose of PD-1/PDL-1 antibody will enroll in cohort B and receive 100mg BID of INCB024360.

Patients enrolled beyond the 6 week period after failing anti-PD-1/PDL-1 will be enrolled in cohort A. Cohort A patients will receive 300mg BID of INCB024360.

Patients must not have active grade 2 autoimmune toxicities attributed to these antibodies at study entry.

- e) 8 weeks after ipilimumab, other CTLA-4 antibody or other immunologically active antibody.

NOTE: Patients receiving prior CTLA-4, anti-PD1 antibody or other immunologic therapy must show evidence of normal pituitary function at baseline and must not have active grade 2 autoimmune toxicities attributed to these antibodies at study entry.

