5. TREATMENT PLAN

5.1 Agent Administration

Patients with surgically incurable stage III or IV melanoma and tissue amenable to serial biopsy will undergo pretreatment tumor biopsy and receive a 3-month course of INCIB024360 administered as a twice daily continuous dosing oral regimen. The

MELITAC 12.1 vaccine has 3 components: 12-MP peptides, Peptide-tet, and Montanide ISA-51 VG vaccine adjuvant, which will be prepared together as an emulsion for administration. Three (3) mL of emulsion will be prepared. Two (2) mL of this emulsion will be administered, with 1 mL at each of 2 vaccine sites. At each site, half of each dose (0.5 mL) will be injected subcutaneously and half (0.5 mL) will be injected intradermally. The remaining 1 mL of the prepared emulsion will be discarded.

On day 21, a week 3 tumor biopsy will be collected and the effects of inhibitor alone on the tumor microenvironment will be evaluated by comparing the pretreatment tumor biopsy to the day 21 tumor biopsy, assessing changes in IHC and gene signatures.

Note: The biopsy on day 21 is mandatory. For patients with only one or two tumors approachable for biopsy, available tumor blocks from prior biopsies can serve as the pretreatment sample.

Also on day 21, a vaccination regimen with MELITAC 12.1 multipeptide vaccine will begin, with vaccines administered on days 21, 28, 35, 56, 77, and 98 (Weeks 3, 4, 5, 8, 11, and 14). MELITAC 12.1, will be administered intradermally/subcutaneously at a fixed dose of 2.0 ml for 6 vaccinations. On day 42, tumor will be biopsied and the effect of continued INCB024360 plus vaccine on the tumor microenvironment will be evaluated by comparing the week 3 tumor biopsy to the week 6 tumor biopsy, assessing changes in IHC and gene signatures.

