6.1 Delayed Visits for Reasons Other Than Toxicity

A schedule for return visits should be established at the first visit. If a participant misses a vaccination, the missed treatment will be administered as soon as possible, so that the subsequent vaccinations are given in the appropriate intervals. Treatment may be continued for an additional time period, if needed. Participants who are vaccinated outside of the established schedule should return to the original schedule as soon as possible.

Table 6.1 defines what constitutes a delayed visit for reasons other than toxicity, whether the participant should continue to be treated, and whether a protocol violation should be reported and recorded. The range of days is counted from the original scheduled date.

Table 6.1. Delayed Visit for Reasons Other than Toxicity

Treatment Period	Range of Days	Participant Treatment	Protocol Deviation
Biopsies	Days -14 to 0*	Biopsies/Labs	
Day 0			
Vaccine 1, Biopsies**			
Day 21 (week 3)	± 2 days	Vaccine/Labs	No
	± 3 to 7 days	Vaccine/Labs	Yes
	± 8 or more days	Labs	Yes
Vaccines 2			
Day 28 (week 4)	± 2 days	Vaccine/ /Biopsy	No
	± 3 to 7 days	Vaccine/ /Biopsy	Yes
	± 8 or more days	Labs	Yes
Vaccine 3			
Day 35 (week 5)	± 2 days	Vaccine/	No

Treatment Period	Range of Days	Participant Treatment	Protocol Deviation
	± 3 to 7 days	Vaccine/	Yes
	± 8 or more days	Labs	Yes
Biopsies**			
Day 42 (week 6)	± 2 days	Labs	No
	± 3 to 7 days	Labs	Yes
	± 8 or more days	Labs	Yes
Vaccines 4–6**			
Days 56, 77, 98 (weeks 8, 11, 14)	± 2 days	Vaccine/Labs***	No
	± 3 to 7 days	Vaccine/Labs***	Yes
	± 8 or more days	Labs	Yes
Biopsies (Optional)**			
Day 112 (Week 16)	± 7 days	Labs	No
	± 8 to 14 days	Labs	Yes
	± 15 or more days	Labs	Yes
Follow-up			
Week 26	± 14 days	Scans/Labs	No
	± 15 days or more	Scans/Labs	Yes

* The pretreatment biopsies should be performed before the first treatment with INCB024360, within 14 days of that start date. For patients with only one or two tumors approachable for biopsy, available tumor blocks from prior biopsies can serve as the pretreatment sample provided at least 20 unstained slides are available.

**A participant will be taken off protocol treatment if more than 1 vaccination is delayed [\pm 3 to 7 days] during the treatment period.

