9. BIOMARKER, CORRELATIVE, AND SPECIAL STUDIES

9.1 **Biomarker Studies**

9.1.1 **Collection of Specimens**

9.1.1.1 **Fine-Needle Aspiration (FNA) Biopsy of Tumor**

FNA biopsy will be prepared as detailed below and stored frozen in liquid nitrogen.

9.1.1.2 **Tumor Biopsies**

Biopsy specimens must include at least 100 mm³ of tumor tissue and ideally 1 cm³ or more. The specimens may be obtained by excisional biopsy, incisional biopsy, or core biopsy. Each surgical specimen or set of core biopsies will be divided into 5 portions: 1/4th will be placed in RPMI and will be processed to yield cryopreserved viable cells for flow cytometric analysis, 1/4th will be fixed in formalin and then embedded in paraffin for histology, 1/6th will be flash frozen in OCT for histology, 1/6th will be flash frozen without medium for Kyn/Trp ratio and 1/6th will be flash frozen in RNA Later for gene expression. (See Laboratory Manual for additional information).

If an archived pre-treatment biopsy is obtained from a formalin-fixed paraffin-embedded (FFPE) tissue block, there must be at least 20 slides available for study.

9.1.1.3 **Blood**

Blood will be collected for serum and PBMC isolation as designated below.

9.1.2 **Processing and Shipping of Specimen(s)**

Tumor specimens will be collected as described above, at the bedside when tumor is biopsied. They will then be processed and shipped as specified below.

9.1.2.1 **Portion for single-cell suspensions**

This will be submitted to mechanical dissociation then, as appropriate, enzymatic digestion (typically collagenase, DNAase, and hyaluronidase). The resulting cells will be collected by centrifugation and cryopreserved viably in 10% dimethyl sulfoxide (DMSO) and either 12.5% HSA (Human serum albumin or 12.5% FCS (Fetal calf serum) using a

controlled-rate freezer. Samples will be stored at -80°C and then batch-shipped on dry ice to the CITN Central Laboratory.

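### The bar on archived baseline blocks that predate another systemic therapy appears only in section 2.4.4 and is missing from the eligibility, treatment, visit-window and calendar text

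*Combined protocol and SAP*

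**What the plan says.** Section 2.4.4 accepts archived tissue as baseline for patients with only one or two approachable tumors, on a condition about treatment: "available tumor blocks from prior biopsies (without intervening systemic treatment) can serve as the pretreatment sample".

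The same allowance appears elsewhere without that condition:

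- The eligibility note in 3.1.2: "available tumor blocks from prior biopsies can serve as the pretreatment sample, but only if formalin-fixed tumor tissue is available and adequate". The adequacy test is at least 20 unstained slides with sufficient tumor.
- The note in 5.1, with no tissue or treatment condition: "available tumor blocks from prior biopsies can serve as the pretreatment sample".
- The Table 6.1 footnote in section 6.1: "available tumor blocks from prior biopsies can serve as the pretreatment sample provided at least 20 unstained slides are available". Footnote a of the section 10 study calendar has the same wording.

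Section 9.1.1.2 adds a quantity rule only: "If an archived pre-treatment biopsy is obtained from a formalin-fixed paraffin-embedded (FFPE) tissue block, there must be at least 20 slides available for study".

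The baseline matters because 5.1 has the inhibitor-alone effect "evaluated by comparing the pretreatment tumor biopsy to the day 21 tumor biopsy". Section 13.2 makes each patient their own control.

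**The concern.** A site screens from section 3 and schedules from sections 5, 6 and 10. None of these states the treatment condition. In 3.1.2 the limiting clause reads as the complete list of requirements, yet it concerns tissue adequacy alone. The one place that protects the baseline is in the background rationale.

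The population makes the gap real. Unresectable stage III or IV patients must have failed at least one non-adjuvant systemic therapy, unless they refused or were ineligible for others. Section 3.1.3.1 adds: "Patients may have had prior systemic therapy without constraint on the number of prior treatment regimens", apart from limits on doxorubicin and pelvic radiation. Cohorts A and B enroll after PD-1/PD-L1 failure, and section 2.4.3 itself says that such blockade can raise T-cell infiltration. By the protocol's own reasoning, an intervening therapy can shift the primary measure.

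Objective 1 has no concurrent control arm. If the block predates another therapy, the within-patient change mixes that therapy and elapsed time with INCB024360, and nothing in the design separates them.

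**Working it through.** **Step 1. The texts side by side.** No figure in the plan bears on this point, so there is none to reproduce.

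| Place | Tissue condition | Condition on treatment after the block |
|---|---|---|
| 2.4.4 | none stated | yes |
| 3.1.2 note | formalin-fixed, at least 20 unstained slides | no |
| 5.1 note | none stated | no |
| Table 6.1 footnote | at least 20 unstained slides | no |
| Calendar footnote a | at least 20 unstained slides | no |
| 9.1.1.2 | at least 20 slides | no |

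One place of six carries the condition. This is an omission, not a pair of opposite statements: following 2.4.4 together with the slide rule satisfies all six.

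**Step 2. Does another rule close the gap?** Take a block, then a systemic therapy that fails, then enrollment.

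- The washouts in 3.1.3.2, 3.2.1 and 3.2.2 count back from enrollment or study entry. They do not look at the block date.
- The 14-day window in 5.4, Table 6.1 and the calendar governs newly taken biopsies. Table 6.1 and the calendar offer the archived block as the alternative.
- No passage limits the age of a block.

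Such a patient meets 3.1.2 and breaks only 2.4.4.

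**Step 3. Illustration on the absolute scale.** The inputs from the plan are 12 patients (13.3) and an SD of 143 cells/mm² (13.2). The number affected, m, and the shift between block and enrollment, s, are assumptions. With no drug effect, the displacement of the mean change is m × s / 12.

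| m | s = 0.5 SD = 71.5 | s = 1 SD = 143 |
|---|---|---|
| 1 | 6.0 | 11.9 |
| 2 | 11.9 | 23.8 |
| 4 | 23.8 | 47.7 |

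These are for a rise. A fall would move the mean the other way. How far depends on how the floor at zero is modeled. If block counts are taken as gamma with mean 137 and SD 143, nominal falls of 71 and 143 average 54.2 and 86.9. For m = 4 the mean then moves by −18.1 (54.2 × 4/12) to −29.0 (86.9 × 4/12).

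**Step 4. Illustration on the relative scale.** Section 13.2 refers to relative increases. For non-zero baselines, if affected pairs carry an assumed r-fold rise, the geometric mean ratio becomes r^(m/12) instead of 1.00.

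| m | r = 1.5 | r = 2 |
|---|---|---|
| 2 | 1.07 | 1.12 |
| 4 | 1.14 | 1.26 |

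**The case against.** The strongest reply is that the safeguard already exists. Section 2.4.4 is current text, and read as a whole the protocol gives one rule: no intervening treatment, and at least 20 slides. On this view only a cross-reference is missing. Registration forms and the Laboratory Manual, which are not in the documents, might also carry the condition. The allowance reaches few patients: they must have only one or two approachable tumors, lack a fresh baseline, have an adequate block, and have been treated since it was taken. Some eligible patients have had no systemic therapy at all. The number affected could be 0 of 12.

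The numbers are also open to challenge. The SD of 143 is a spread across 148 metastases, not a within-patient change after therapy. The smaller figures for a fall arise only because the gamma distribution was assigned to the block. Assigned to the enrollment count, it would put the floor on the rise instead.

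Much of this stands. The texts can be read together, exposure is uncertain, and the figures show scale only; no weight should rest on the rise-fall asymmetry. None of it removes the omission from the text that sites use to screen, and unseen documents cannot be credited with a condition the protocol's eligibility section lacks.

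**Conclusion.** The point holds as an omitted condition, and it should be fixed. A block that predates a failed therapy is acceptable under 3.1.2, 5.1, Table 6.1 and the calendar, and unacceptable under 2.4.4.

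What is at risk is the meaning of the estimated change for Objective 1. Section 11 calls the endpoints exploratory and 9.2.1 describes a descriptive analysis, so no stated error rate is affected. Objective 2 compares week 3 with week 6, does not use the baseline block, and is untouched.

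The true direction and size are unknown. The documents give neither a count of archived blocks nor a shift. Under the assumed rises, 2 to 4 affected patients of 12 would displace the mean change by 12 to 48 cells/mm², set against the change of about 143 that 13.2 offers as an example of a large one. Confidence is high in the textual gap, and it does not extend to any particular bias.

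**What to change.** Carry the parenthetical condition from 2.4.4 into the 3.1.2 note, the 5.1 note, the Table 6.1 footnote and calendar footnote a, and cross-refer to it in 9.1.1.2. Record two items for every archived baseline: the block date, and any systemic therapy between that date and enrollment.

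The cost is one existing phrase in four places, one cross-reference and two data items. The downside is that a few patients whose only baseline is an older block would have no usable one, as 2.4.4 already implies. Section 13.3 replaces patients without adequate sampling for immune responses; the sponsor should say whether that covers tumor samples.

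Optionally, summarize the pretreatment-to-day-21 change for patients with a fresh baseline. Once pre-therapy blocks are barred, this mainly addresses elapsed time, and it would be imprecise. The 95% half-width is t(0.975, n−1) × SDd / √n, with SDd = 143 × √(2(1−ρ)) and the pre/post correlation ρ assumed. At ρ = 0.5 it is 91 cells/mm² for 12 pairs, 120 for 8 and 150 for 6. At ρ = 0 it is 128, 169 and 212.
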